8.3.1 Product Complaints or Medication Errors

A medication error is a preventable event that involves an identifiable patient and that leads to inappropriate medication use, which may result in patient harm. While overdoses and under doses constitute medication errors, doses missed inadvertently by a patient do not. Individuals who identify a potential medication error situation should immediately contact PrECOG and report the event.

Product complaints and medication errors in and of themselves are not AEs. If a product complaint or medication error results in an SAE, an SAE form should be completed and sent to PrECOG.

8.4 Reporting of Other Second Primary Cancers

New cancers are those that are not the primary reason for administration of study treatment and have been identified after inclusion of the patient into the clinical study.

All cases of new primary cancers that occur during or after protocol treatment must be reported to PrECOG on a Second Primary Cancer form within 30 days of diagnosis, regardless of relationship to protocol treatment. Secondary primary malignancies should also be reported as a SAE. The SAE form is not for use for reporting recurrence or

development of metastatic disease. A copy of the pathology report, if applicable, should be sent, if available.

NOTE: Once data regarding survival and remission status are no longer required by the protocol, no follow-up data should be submitted.

8.5 Procedures in Case of Pregnancy

Prior to study enrollment, women of childbearing potential (WOCBP) and male patients with a female partner of childbearing potential must be advised of the importance of avoiding pregnancy during trial participation and the potential risk factors for an unintentional pregnancy, documented in the informed consent. In addition, all WOCBP should be instructed to contact the Investigator immediately if they suspect they might be pregnant (e.g., missed or late menstrual period) at any time during study participation.

Pregnancy of a female patient or the female partner of a male patient occurring while the patient is receiving study drug or within 3 months after the patient's last dose of study drug will be reported to PrECOG on a Pregnancy Form within 24 hours of the investigator's knowledge of the pregnancy.

All reports of congenital abnormalities/birth defects and spontaneous miscarriages should also be reported and handled as SAEs. Elective abortions without complications should not be handled as AEs.

The outcome of all pregnancies (spontaneous miscarriage, elective termination, normal birth including health of the newborn or congenital abnormality) must be followed and documented on the Pregnancy Form even if the subject was discontinued from the study treatment. Should pregnancy occur during a subject's participation, the subject will immediately be discontinued from the treatment and followed per protocol.

The study-specific Pregnancy Form can be found in the Study Reference Manual.

9. Measurement of Effect

LUGANO Classification

All disease response evaluation shall occur according to the Lugano classification³⁵.

9.1 Scheduled Restaging Studies

All patients shall complete a PET/CT at the time of study enrollment. Thereafter, restaging shall include CT chest/abdomen/pelvis after cycles 3, 6, 9, and 12, and then every 6 months while on study therapy. PET/CT or MRI may be substituted for CT at the discretion of the treating investigator, especially in cases where lesions are not readily noted on CT. Patients who discontinue study therapy for reasons other than disease progression shall have CT's performed every 6 months until progression and/or initiation of a new therapy.

All patients with suspected CR based on routine restaging should have a PET/CT performed to confirm CR.

9.2 Complete Response (CR)

In order to satisfy the criteria for a complete response, patients who undergo CT scan only must meet the following criteria:

- Target nodes/nodal masses must regress to ≤ 1.5 cm in longest transverse diameter.
- No extralymphatic sites of disease.
- Absent non-measured lesions.
- All organ enlargement must be regressed to normal.
- No new lesions.
- Bone marrow must be normal by morphology (must be evaluated at the time of suspected CR in patients with a positive bone marrow at enrollment).

Patients undergoing a PET/CT must meet the following criteria:

- Deauville score of 1, 2 or 3 on the 5-point scale.
- No new lesions.
- No evidence of FDG avid disease in the bone marrow.

NOTE: ALL PATIENTS WITH SUSPECTED CR WHO HAD BONE MARROW INVOLVEMENT AT SCREENING MUST UNDERGO A BONE MARROW BIOPSY TO CONFIRM RESPONSE.

9.3 Partial Response (PR)

Patients undergoing a CT must meet the following criteria for PR:

- $\geq 50\%$ decrease in the sum of the product of the diameters (SPD) of up to 6 target measurable nodes and extranodal sites.
- Lesions too small to measure on CT should be considered 5 mm x 5 mm as the default value.
- Lesions that are no longer visible should be considered 0 mm x 0 mm.
- Non-measured lesions should be absent/normal or regressed, but without increase.
- Spleen, if previously enlarged, must have regressed by $>50\%$ in length beyond normal.

Patients undergoing PET/CT must meet the following criteria for PR:

- Deauville score of 4 or 5 with reduced uptake compared to baseline and residual masses of any size.

- Bone marrow with residual uptake higher than uptake in normal marrow but reduced compared to baseline (diffuse uptake compatible with reactive changes from chemotherapy is allowed). If there are persistent focal changes in the marrow in the context of a nodal response, consideration should be given to further evaluation with MRI or biopsy or an interval scan.

9.4 No Response/Stable Disease (SD)

Patients undergoing CT must meet the following criteria for SD/No response:

- <50% decrease from baseline in SPD of up to 6 dominant, measurable nodes and extranodal sites; no criteria for progressive disease are met.
- No increase of non-measured lesions or organ enlargement consistent with progression.

Patients undergoing PET/CT must meet the following criteria for SD/No response:

- Deauville score of 4 or 5 with no significant change in FDG uptake from baseline at interim or end of treatment.
- No change in FDG activity of bone marrow from baseline.

9.5 Progressive Disease (PD)

Patients undergoing CT must meet one of the following criteria for PD:

- An individual node/lesion must be abnormal with the following:
 - Longest diameter >1.5 cm and
 - Increase by $\geq 50\%$ from the cross product of the longest diameter and perpendicular diameter nadir and
 - Increase in the longest diameter or shortest diameter from nadir:
 - 0.5 cm for lesions ≤ 2 cm
 - 1.0 cm for lesions >2 cm
- For patients with splenomegaly, the splenic length must increase by $>50\%$ of the extent of its prior increase above baseline. If no prior splenomegaly, it must increase by at least 2 cm from baseline.
- New or recurrent splenomegaly.
- New or clear progression of pre-existing non-measured lesions.
- Regrowth of previously resolved lesions.
- A new node >1.5 cm in any axis.
- A new extranodal site >1.0 cm in any axis; if <1.0 cm in any axis, its presence must be unequivocal and must be attributable to lymphoma.
- Assessable disease of any size unequivocally attributable to lymphoma.
- New or recurrent bone marrow involvement.

Patients undergoing PET/CT must meet one of the following criteria for PD:

- Deauville score of 4 or 5 with an increase in intensity of uptake from baseline.
- New FDG-avid foci consistent with lymphoma (If uncertain regarding the etiology of a new lesion, biopsy or interval scan may be considered).

NOTE: Patients with isolated lymphocytosis shall not constitute progression in the absence of other findings.

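### On CT, one PD criterion in Section 9.5 is not limited to new disease, so residual lymphoma counts as progression; separately, Section 9.3 lets PR and PD hold together

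*Protocol*

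**What the plan says.** Section 9 of the Protocol adopts the Lugano classification and then writes out its own criteria for each category, with separate CT and PET/CT lists. Section 9.1 makes CT the default restaging method (after cycles 3, 6, 9 and 12, then six-monthly). PET/CT or MRI may replace it at the investigator's discretion.

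- **PD on CT (9.5).** The lead-in is "Patients undergoing CT must meet one of the following criteria for PD", so one bullet is enough. Among the bullets are "A new node >1.5 cm in any axis", then "A new extranodal site >1.0 cm in any axis; if <1.0 cm in any axis, its presence must be unequivocal", and then, standing alone, "Assessable disease of any size unequivocally attributable to lymphoma".
- **SD on CT (9.4).** The size condition is "<50% decrease from baseline in SPD of up to 6 dominant, measurable nodes and extranodal sites", and it is joined to the requirement that "no criteria for progressive disease are met".
- **SD on PET/CT (9.4).** A separate branch: "Deauville score of 4 or 5 with no significant change in FDG uptake from baseline at interim or end of treatment", with unchanged marrow activity.
- **PR on CT (9.3).** At least a 50% fall in the target SPD, a spleen condition, and "Non-measured lesions should be absent/normal or regressed, but without increase". Neither the CT nor the PET/CT list for PR mentions new lesions or excludes patients who meet PD.
- **CR (9.2).** Both lists exclude new lesions.

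Section 3.14 requires measurable disease at entry. Section 7.1, item 1, ends protocol therapy at progression per Lugano or at clinical progression. ORR and PFS are phase II secondary objectives (2.2.2, 12.2.2).

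**The concern.** Every other CT bullet in Section 9.5 asks for change: growth from nadir, a larger spleen, a new or recurrent finding, clear progression, or regrowth. The quoted bullet asks only that lymphoma be present and assessable. Patients in PR or SD usually still have lymphoma, so the bullet as worded catches patients whom Sections 9.3 and 9.4 place elsewhere.

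The PR definition has a second gap that does not depend on that bullet. Nothing in Section 9.3 removes a patient whose target lesions shrink while a new lesion appears.

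The categories feed directly into results. The PD date sets PFS, PR counts towards ORR, and PD ends protocol therapy. If sites fill in the missing words differently, the same scan can be a response at one site and progression at another.

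**Working it through.** The protocol gives no figure for this point, so the check applies the written CT rules to example patients.

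**1. Stable residual disease on CT.** Illustrative patient: one target node known to be lymphoma, 4.0 x 3.0 cm at baseline and 3.8 x 3.0 cm at restaging, nothing new.

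- Baseline product: 4.0 x 3.0 = 12.0 cm². Restaging product: 3.8 x 3.0 = 11.4 cm².
- Decrease: (12.0 - 11.4) / 12.0 = 5%. This is below 50%, so the SD size condition is met and PR is not.
- Growth, regrowth and new-lesion bullets of 9.5: none met.
- Quoted bullet: met, because assessable lymphoma is present.

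| Reading of the bullet | PD | SD |
|---|---|---|
| As written | yes | no |
| Limited to new disease | no | yes |

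The result is general. A decrease of less than 50% from measurable disease leaves disease on the scan. If that disease is unequivocally lymphoma, the bullet applies, PD is met, and 9.4 then rules out SD.

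**2. Partial response on CT with residual lymphoma.** A 60% SPD decrease meets the PR size condition. Lymphoma that remains assessable also meets the quoted bullet. Section 9.3 does not exclude PD, so both categories hold.

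**3. Response plus a new node, leaving the quoted bullet aside.** Target SPD falls by at least 50% and a new 2 cm node appears.

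- PR on CT: the size condition is met. The item on non-measured lesions does not clearly remove the patient, because a 2 cm node is measurable.
- PD on CT: met through the new-node bullet (2 cm exceeds 1.5 cm).

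The PET/CT lists overlap in the same way. Section 9.3 accepts a score of 4 or 5 with reduced uptake as PR. Section 9.6 includes new lesions in score 5, and Section 9.5 calls a new FDG-avid focus consistent with lymphoma PD.

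**4. Weight of one patient.** With 31 eligible, treated patients planned for Cohort A, each patient moved between PR and PD shifts ORR by 1/31 = 3.2 percentage points.

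**5. Primary test.** Section 12.2.1 rejects the null with 10 or more CRs in 31. The exact binomial probability of X >= 10 is 0.0975 at p = 0.21 and 0.857 at p = 0.40, matching the stated 10% and 86%. The CR criteria do not use the quoted bullet, so these figures stand.

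**The case against.** The strongest reply is that nobody would apply the bullet literally. If any residual lymphoma were PD, the growth and size thresholds in the rest of Section 9.5 would be nearly pointless. Sections 9.3 and 9.4 plainly treat residual disease as compatible with PR and SD. The bullet follows items on regrown and new lesions, and Sections 9 and 7.1 name Lugano as the standard. This stands as evidence of intent: new disease is the likely meaning. It does not cure the text, because no section limits the bullet. The fallback in Section 12.2.1 does not help either. It defers to standard criteria under citation 34, and entry 34 in Section 15 is a phase I multiple myeloma dosing study.

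A second reply is that a new node above 1.5 cm is expressly PD, so a site would have to ignore a stated criterion to report PR, and that precedence between categories can be left to an analysis plan. The first part is fair and makes such errors less likely. On the second, the point is not a missing derivation rule. The protocol's stated definitions overlap, and Section 9.3 lacks safeguards that 9.2 and 9.4 carry.

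A third reply is that the impact is limited: the primary endpoint is CR rate, ORR is descriptive, and PFS is a Kaplan-Meier estimate without a test. That is correct and bounds the importance of the point.

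**Conclusion.** The concern holds for the CT criteria as written. On CT, residual lymphoma satisfies a PD criterion, SD cannot be met, and PR overlaps with PD. The PR list also overlaps with PD whenever a qualifying new lesion appears, whatever the quoted bullet means. This rests on CT being the restaging method and on the residual lesion being judged unequivocally lymphoma.

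The effect is on PFS, on ORR (3.2 percentage points per misclassified patient among 31) and on the progression trigger. The documents give no basis for estimating how many patients would be misclassified. The CR criteria and the alpha and power of the primary test are unchanged. A premature PD call could end therapy before a later CR within the 12-month window, but the size of that indirect effect cannot be derived.

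Two stronger readings are not supported:

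- A reader might infer that SD can never be assigned. The PET/CT branch of SD does not use the quoted bullet, and PET/CT may replace CT.
- A reader might subtract the 40% target CR rate from 100% and infer that at least 60% of Cohort A would be PD at the cycle 3 scan, with median PFS near 12 weeks (3 x 28 = 84 days). The 40% is a design target for CR within 12 months, not an expected rate at the first scan. The inference also needs CT for every patient and a literal reading that sites are unlikely to follow.

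**What to change.** Reconcile Sections 9.3, 9.4 and 9.5 with each other and with the Lugano classification named in Section 9:

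- In the 9.5 CT list, state that the bullet on assessable disease of any size refers to new disease.
- In 9.3, add to both the CT and the PET/CT list that there are no new lesions and that none of the PD criteria is satisfied.
- In 12.2.1, correct the citation attached to the standard criteria for progression.

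The cost is a few words in the response sections, one corrected citation and a short clarification to sites. No new data, scans or procedures are needed, and no design figure changes.

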9.6 Criteria for PET/CT Reporting

Patients who undergo PET/CT as part of their interim, on-treatment, and end of treatment staging assessments should be assessed according to the following scoring system.

1. No uptake above background.
2. Uptake \leq mediastinum.
3. Uptake $>$ mediastinum but \leq liver.
4. Uptake moderately greater than liver.
5. Uptake markedly higher than liver and/or new lesions.

X New areas of uptake unlikely to be related to lymphoma.

For further information regarding the Deauville scoring system, please refer to Barrington et al, J Clin Oncol 2014³⁵.

10. Study Parameters

1. All pre-study scans should be done \leq 4 weeks prior to registration.
2. All other pre-study assessments should be done \leq 2 weeks prior to registration.

Procedures	Screening	Cycle 1* (1 cycle=28 Days)				Cycle 2-Cycle 6*				Cycle 7 and Subsequent Cycles ^{12*}	Every 3 Cycles*	Off Treatment ¹⁴	Follow- Up ¹⁶
		Day 1 +/- 1 day	Day 8 +/- 1 day	Day 15 +/- 1 day	Day 22	Day 1 +/- 3 days	Day 8 +/- 3 days	Day 15 +/- 3 days	Day 22 BREAK				
Written Informed Consent	X												
Disease Characteristics ¹	X												
Medical/Surgical History	X												
Assessment of Baseline Signs & Symptoms	X												
Height	X												
Physical Exam including Weight	X	X		X		X				X ¹²		X	
Vital Signs (Temperature, Pulse, Blood Pressure)	X	X		X		X				X ¹²		X	
Performance Status	X	X				X				X ¹²		X	
CBC/Differential/Platelets ²	X	X		X	X	X ²		X ²		X ²		X	
Chemistry ³	X	X		X		X ³				X ³		X	
PT/INR	X												
Lactate Dehydrogenase (LDH)	X												
Vitamin D Level ⁴	X												
Peripheral Blood Flow Cytometry	X												
Serum Pregnancy Test ⁵	X												
PET/CT	X												
Chest/Abdomen/Pelvic MRI or CT ⁶										X ¹³		X	
Bone Marrow Aspirate and Biopsy ⁷	X											X ⁷	

Procedures	Screening	Cycle 1* (1 cycle=28 Days)				Cycle 2-Cycle 6*				Cycle 7 and Subsequent Cycles ^{12*}	Every 3 Cycles*	Off Treatment ¹⁴	Follow- Up ¹⁶
		Day 1 +/- 1 day	Day 8 +/- 1 day	Day 15 +/- 1 day	Day 22	Day 1 +/- 3 days	Day 8 +/- 3 days	Day 15 +/- 3 days	Day 22 BREAK				
Bone Marrow Conventional Cytogenetics and FISH ⁸	X												
Pathology Review with Ki67 Assessment ⁹	X												
Research Specimens ¹⁰		X ¹⁰									X ¹⁰	X ¹⁰	
Treatment Administration ¹¹		X	X ¹¹	X		X ¹¹	X ¹¹	X ¹¹		X ¹¹			
Concomitant Medication Review	X	X		X		X				X ¹²		X	
Adverse Events Assessment		X		X		X				X ¹²		X ¹⁵	
Survival Status													X

* **Scheduled Visits:** +/-3 day window is allowed for scheduled ixazomib therapy, required tests and/or visits except as otherwise noted. Delay due to holidays, weekends, bad weather or other unforeseen circumstances will be permitted.

1 Record date of diagnosis and stage.

2 CBC with differential and platelet count which includes WBC, ANC, Platelets, Hemoglobin, and Hematocrit required as noted below.

Phase I: Days 1, 8, 15 and 22 of Cycle 1; Days 1 and 15 of Cycle 2 and Cycle 3 (patients with ANC <1000 and/or platelets <100,000/mm³ on Day 15 should have blood counts done on Day 22 for Cycle 2 and 3 only); and Day 1 of subsequent cycles. **Phase I completed November 25, 2019.**

Phase II: Days 1 and 15 of Cycle 1 for which a clinic visit is required. Patients will be required to be seen in clinic on Day 1 of Cycles 2-7, then every 3 cycles thereafter. Labs are only required on the days patients are seen in clinic.

Results known prior to treatment administration. Patients experiencing cytopenias should have additional labs drawn as clinically indicated at the discretion of the treating physician.

3 Albumin, BUN/creatinine, uric acid, sodium, potassium, chloride, glucose, calcium, alkaline phosphatase, AST, ALT, total bilirubin, and total protein. Days 1 and 15 of Cycle 1 for which a clinic visit is required. Patients will be required to be seen in clinic on Day 1 of Cycles 2-7, then every 3 cycles thereafter. Labs are only required on the days patients are seen in clinic.

NOTE: Patients with a history of hepatitis B or C must have a negative peripheral blood Polymerase Chain Reaction (PCR) and may not be positive for Hepatitis B surface antigen.

- 4 25(OH) Vitamin D level.
- 5 Required for sexually active females of child-bearing potential.
- 6 PET/CT may be substituted for CT Chest/Abdomen/Pelvis at the discretion of the investigator.
- 7 Bone Marrow Biopsy to include: Aspirate and core biopsy morphologic evaluation and flow cytometry. Bone marrow biopsy will be repeated at the time of suspected CR for patients with involvement at the time of enrollment. Optional bone marrow biopsies and aspirates will be performed as clinically indicated at the end of therapy and/or time of progression.
- 8 Bone marrow samples will be sent for conventional cytogenetics, FISH for t(11;14) and FISH for del(17p) [conventional cytogenetics, FISH for t(11;14) and FISH for del(17p) may also be done on tumor tissue samples (nodal or extranodal) in lieu of or in addition to bone marrow review].
- 9 Pathologists at the participating site must review available tissue samples to confirm the diagnosis of MCL. If a pathology review has already been completed in the routine care of the patient, then additional review is not required. All patients should have an assessment of Ki67 performed on available tissue. Tissue used for pathology review should ideally be from the time of relapse but pre-treated tissue can be used if that is the only available sample.
- 10 Research samples shall be obtained at the time of screening/study entry, after cycle 3, at time of suspected CR, and at the end of therapy or time of progression. Refer to Section 13 for details.

Screening/Study Entry

Peripheral Blood: Two 6 mL in EDTA tubes

Bone Marrow: One 10 mL in EDTA tube

FFPE: Block preferred or 1 H&E slide plus 10 unstained slides

After Cycle 3 (up to 5 days before Cycle 4, Day 1)

Peripheral Blood: Two 6 mL in EDTA tubes

At time of Suspected CR

Peripheral Blood: Two 6 mL in EDTA tubes

End of Therapy/At Time of Progression (within 45 days of last dose of study medication)

Peripheral Blood: Two 6 mL in EDTA tubes

NOTE: If sufficient bone marrow and tumor tissue are available, submission is mandatory). No bone marrow biopsy/aspirate or tissue biopsy should be performed solely for the purposes of obtaining research samples.

- 11 Patients will receive ixazomib orally on days 1, 8, and 15 of each 28 day cycle (1 cycle=28 days) [Section 6.1.1 for dosing administration]. Ixazomib shall be administered in the clinic on Cycle 1, Day 1 and Cycle 1, Day 15 (Day 8 can be administered at home). For subsequent cycles, ixazomib doses on Days 8 and 15 can be administered at home. Ixazomib Medication Diary will be reviewed for compliance and collected every cycle after Cycle 1 (Appendix III). Ibrutinib shall be administered orally daily on days 1-28 [Section 6.1.2 for dosing administration]. Ibrutinib Medication Diary will be reviewed for compliance and collected every cycle (Appendix IV). See Section 6.2 for Phase I and Section 6.3 for Phase II dosing instructions and Section 6.5 for dose delays/modifications.

NOTE: If patient continues on study therapy after Cycle 6, the visit schedule may be increased to every 3 cycles starting with Cycle 7 and study medication will be dispensed for 3 cycles. Medication Diaries will be collected every 3 cycles when patient returns to clinic.

- 12 If patient continues on study therapy after Cycle 6, the visit schedule may be increased from 4 to 12 weeks starting with Cycle 7 while receiving study therapy (Scan schedule will remain unchanged, see footnote 13). Physical exam with weight, vital signs, performance status, blood work, concomitant medication review and adverse events assessment will be performed every 12 weeks (Day 1 of every 3 cycles).

- 13 While on treatment, patients shall undergo CT chest/abdomen/pelvis (or PET/CT or MRI as clinically indicated per investigator discretion) after cycles 3, 6, 9, 12 and subsequently every 6 months while on study therapy. Scans should be performed during the 7 days preceding the following cycle (i.e., within 7 days of Cycle 4, Day 1). **Patients with suspected CR should undergo PET/CT to confirm this. This can be done within 21 days of the restaging CT that initially demonstrates potential CR.**
- 14 Thirty (30) days +/- 7 days after last dose of study therapy. If patient is removed from treatment for reason(s) other than progression, follow with regular tumor assessments per standard of care until progression or start of new treatment. Once a patient has initiated a new therapy, no further study-related imaging assessments for this study are required.
- 15 Patients will be followed for adverse events for 30 days after their last dose of study medication. However, an adverse event occurring at any time after discontinuation of study therapy that is felt to be at least possibly related to study therapy should be recorded.
- 16 There are no study-related visits required after the end of treatment visit. However, as available to the participating investigators, survival status every 6-12 months for participating patients should be updated and recorded. In addition, the first subsequent therapy shall be reported.

11. Drug Formulation and Procurement

